#### **4.1.1.2 Cancer-Related Inclusion Criteria**

Patients must meet the following cancer-related criteria for study entry (for cohort-specific inclusion criteria, see Section 4.1.3):

- Patients must have measurable disease by CT or MRI scan per RECIST v1.1.
- Availability to provide a representative tumor specimen biopsy:

Baseline tumor tissue samples will be collected from all patients, preferably by means of a biopsy performed at study entry. *For patients with SCCHN or RCC, histologic samples are required. For patients with UC, cytological or histologic samples are acceptable.* Archival tumor tissue may be submitted after Medical Monitor approval has been obtained.

A formalin-fixed, paraffin-embedded tumor specimen in a paraffin block (preferred) or at least 15 slides (20 preferred) containing unstained, freshly cut, serial sections is recommended to be submitted along with an associated pathology report prior to study enrollment. If a limited number of slides are available, the patient may still be eligible for the study, after discussion with and approval by the Medical Monitor.

- Evidence of tumor progression on or after the last treatment regimen received and within 6 months prior to study enrollment
- For women of childbearing potential: agreement to remain abstinent (refrain from heterosexual intercourse) or use a non-hormonal contraceptive method with a failure rate of  $< 1\%$  per year during the treatment period and for at least 5 months after the last dose of atezolizumab and within 3 months after the last dose of cobimetinib. *Women must refrain from donating eggs during this same period.*

A woman is considered to be of childbearing potential if she is postmenarcheal, has not reached a postmenopausal state ( $\geq 12$  continuous months of amenorrhea with no identified cause other than menopause), and has not undergone surgical sterilization (removal of ovaries and/or uterus).

Examples of contraceptive methods with a failure rate of < 1% per year include bilateral tubal ligation, male sterilization, and copper intrauterine devices.

The reliability of sexual abstinence should be evaluated in relation to the duration of the clinical trial and the preferred and usual lifestyle of the patient. Periodic abstinence (e.g., calendar, ovulation, symptothermal, or postovulation methods) and withdrawal are not acceptable methods of contraception.

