  - Patients who are receiving bisphosphonate therapy for other reasons (e.g., bone metastasis or osteoporosis) and who do not have a history of clinically significant hypercalcemia are eligible for the study.
- Active or untreated CNS metastases
  - Patients with treated and asymptomatic CNS metastases are eligible, if they meet all of the following:
    - Evaluable or measurable disease outside the CNS
    - No metastases to midbrain, pons, medullar or within 10 mm of the optic nerves and chiasm
    - No history or evidence of intracranial hemorrhage or spinal cord hemorrhage
    - No evidence of clinically significant vasogenic edema
    - No corticosteroids for ≥ 2 weeks; anti-convulsant medications at a stable dose are allowed
    - No evidence of clinical and radiographic disease progression in the CNS for ≥ 3 weeks after radiotherapy or surgery
- Pregnancy or breastfeeding, or intending to become pregnant during the study
  - Women of childbearing potential must have a negative serum pregnancy test result within 14 days prior to initiation of study treatment.

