### **4.5 STUDY ASSESSMENTS**

Refer to [Appendix 1](#) for the schedule of activities to be performed during the study. All activities must be performed and documented for each patient. Patients will be closely monitored for safety and tolerability throughout the study. Patients should be assessed for toxicity prior to each dose; dosing will occur only if the clinical assessment and local laboratory test values are acceptable.

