##### **4.5.6.2 Treatment (Local Laboratory)**

Samples for the following laboratory tests during treatment will be sent to the study site's local laboratory for analysis:

- Hematology: WBC count, RBC count, CBC, hemoglobin, hematocrit, count with differential (neutrophils, eosinophils, basophils, monocytes, and lymphocytes)

- Serum chemistry panel: glucose, BUN or urea, creatinine, sodium, potassium, magnesium, calcium, phosphorus, total bilirubin, ALT, AST, ALP, CPK, and others according to the schedule of activities (see [Appendix 1](#))
- Urine pregnancy test for women of childbearing potential
- Thyroid function test

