## Appendix 1 Schedule of Activities (cont.)

ADA=anti-drug antibody; Discon=discontinuation; ECHO=echocardiogram; ECOG=Eastern Cooperative Oncology Group; eCRF=electronic Case Report Form; FU=follow-up; HBcAb=hepatitis B core antibody; HBsAg=hepatitis B surface antigen; HBV=hepatitis B virus; HCV=hepatitis C virus; IRR=infusion-related reactions; LVEF=left ventricular ejection fraction; MUGA=multiple-gated acquisition; PBMC=peripheral blood mononuclear cell; PK=pharmacokinetic; RECIST v1.1=Response Evaluation Criteria in Solid Tumors, Version 1.1; T3=triiodothyronine; T4=thyroxine; Tx=treatment; WGS=whole genome sequencing.

Notes: All assessments should be performed within  $\pm 3$  days of the scheduled visit, unless otherwise specified. On treatment days, all assessments should be performed prior to dosing, unless otherwise specified. On treatment days, pre-infusion laboratory samples should be drawn 0–4 hours before the start of infusion, and post-infusion laboratory samples should be drawn 0–30 minutes after the end of infusion, unless otherwise specified.

Assessments shaded in gray should be performed as scheduled, but the associated data do not need to be recorded on the eCRF (except in the case of an adverse event).

- a Results of standard-of-care tests or examinations performed prior to obtaining informed consent and within 28 days prior to Day 1 may be used; such tests do not need to be repeated for screening.
- b Patients who discontinue study drug will return to the clinic for a treatment discontinuation visit *within 30 (+ 3) days after the last dose*. The visit at which response assessment shows progressive disease may be used as the study discontinuation visit.
- c Visit not specified by the protocol. Assessments should be performed as clinically indicated.
- d Required follow-up information will be collected via telephone calls and/or clinic visits every 3 months until death, loss to follow-up, or study termination by the Sponsor.
- e Informed consent must be documented before any study-specific screening procedure is performed and may be obtained up to 28 days before initiation of study treatment.

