### Schedule of Activities (cont.)

- 
- k Evaluation of LVEF by ECHO or MUGA scan must be performed at the following timepoints only for patients on cobimetinib: at screening; on Day 1 of Cycle 2 ( $\pm 1$  week); on Day 1 of Cycles 5, 8, 11, 14, 17, and every 3 treatment cycles thereafter (i.e., Cycles 20, 23, 26, etc.;  $\pm 2$  weeks for each); and at treatment discontinuation visit evaluation (unless evaluation performed within the previous 12 weeks showed no clinically significant findings and/or changes from baseline).
- l Tumor assessments will continue until disease progression per RECIST v1.1 or immune-modified RECIST unless patient continued treatment, loss of clinical benefit (for patients who continue treatment after disease progression according to RECIST v1.1 or immune-modified RECIST), withdrawal of consent, study termination by the Sponsor, or death, whichever occurs first. Patients who discontinue treatment for reasons other than disease progression (e.g. toxicity) will continue scheduled tumor assessments until disease progression, withdrawal of consent, study termination by Sponsor, or death, whichever occurs first.
- m All patients will be tested for HIV prior to the inclusion into the study and HIV-positive patients will be excluded from the study. HBV serology will include HBsAg, antibodies against HBsAg, and total HBcAb antibody (anti-HBcAb). HBV DNA should be obtained prior to enrollment if patient has a negative serology for HBsAg and a positive serology for anti-HBcAb. HCV serology will include HCV antibody (anti-HCV). HCV RNA should be obtained prior to enrollment if patient tests positive for anti-HCV.
- n Thyroid-function testing (thyroid-stimulating hormone, free T3 [or total T3 for sites where free T3 is not performed], and free T4) collected on Day 1 of Cycles 1–5, and every 2 cycles thereafter (i.e., Day 1 of Cycles 7, 9, 11, etc.) for patients on atezolizumab.

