- o Ophthalmologic examination must be performed at the following timepoints only for patients on cobimetinib: at screening; on Day 1 of Cycle 2 ( $\pm 1$  week); on Day 1 of Cycles 5, 8, and 11 (every 3 treatment cycles;  $\pm 2$  weeks); on Day 1 of Cycles 15, 19, and 23 (every 4 treatment cycles;  $\pm 2$  weeks); on Day 1 of Cycles 29, 35, 41, 47, and every 6 treatment cycles thereafter (i.e., Cycles 53, 59, 65, etc.;  $\pm 2$  weeks for each); and at treatment discontinuation visit evaluation (unless evaluation performed within the previous 12 weeks showed no clinically significant findings and/or changes from baseline).
- p All women of childbearing potential will have a serum pregnancy test at screening. Urine pregnancy tests will be performed on Day 1 ( $\pm 2$  weeks) of every cycle. If a urine pregnancy test is positive, it must be confirmed by a serum pregnancy test.
- q Includes dipstick (pH, specific gravity, glucose, protein, ketones, and blood) and microscopic examination (sediment, RBCs, WBCs, casts, crystals, epithelial cells, and bacteria).
- r Includes any medication (e.g., prescription drugs, over-the-counter drugs, herbal or homeopathic remedies, nutritional supplements) used by a patient from 7 days prior to initiation of study drug until 30 days after the last dose of study drug.
- s After informed consent has been obtained but prior to initiation of study drug, only serious adverse events caused by a protocol-mandated intervention should be reported. After initiation of study drug, all adverse events will be reported until 30 days after the last dose of study drug or initiation of new anti-cancer therapy, whichever occurs first. After this period, all deaths, regardless of cause, should be reported. After this period, the Sponsor should be notified if the investigator becomes aware of any serious adverse event that is believed to be related to prior study drug treatment (see Section 5.6). The investigator should follow each adverse event until the event has resolved to baseline grade or better, the event is assessed as stable by the investigator, the patient is lost to follow-up, or the patient withdraws consent. Every effort should be made to follow all serious adverse events or adverse events of special interest considered to be related to study drug or trial-related procedures until a final outcome can be reported.

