## Appendix 1 Schedule of Activities (cont.)

- 
- t Biopsy schedule for patients in Cohorts 1–6. Please see different biopsy schedule listed in the table for the biopsy cohort (Cohort 7). Fresh baseline tumor tissue collected during screening (or archival if fresh tumor biopsy cannot be performed); optional on-treatment biopsy at Cycle 1, Day 15 ( $\pm 5$  days); mandatory biopsy at progression if clinically feasible.
- u Mandatory pre-treatment biopsy
- v Biopsy Cohort 7, mandatory tumor biopsy done between Days 10 and 14 of Cycle 1.
- w Biopsy Cohort 7, second (mandatory) on-treatment biopsy will be done during Cycle 2, approximately 4–6 weeks after the first dose of atezolizumab.
- x Biopsy Cohort 7, optional post-treatment biopsy at the time of radiographic progression.
- y Biomarkers are collected until Cycle 3, Day 1 (including that visit) and then at treatment discontinuation.
- z Urine samples will be collected for urothelial carcinoma patients only: screening on Day 1 of Cycle 1; on Day 1 of Cycle 3; and at treatment discontinuation visit only.
- aa The initial dose of atezolizumab will be delivered over 60 ( $\pm 15$ ) minutes. If the first infusion is well tolerated, all subsequent infusions will be delivered over 30 ( $\pm 10$ ) minutes until loss of clinical benefit. Study drug administration may be  $\pm 7$  days.
- bb For patients in Cohorts 1–6 only.
- cc All patients will receive cobimetinib at a dose of 60 mg (three 20-mg tablets) orally once a day on Days 1–21 of each 28-day cycle. At least 7 days off cobimetinib are required prior to starting a new treatment cycle. Cobimetinib should be taken approximately the same time each day, and no later than 4 hours after the scheduled time.
-

## Appendix 2

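### The ±2-week window on the per-cycle urine pregnancy test lets a cycle's test fall after 14 of its 21 cobimetinib doses and leaves up to 56 days between tests

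*Combined protocol and SAP*

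**What the plan says.** The Appendix 1 schedule marks the pregnancy test at screening, on Day 1 of each cycle and at treatment discontinuation. The Day 1 columns carry ±3 days, but the notes to the table let a more specific window override that default. Footnote p does so: "Urine pregnancy tests will be performed on Day 1" of every cycle, ±2 weeks. A positive urine result must be confirmed in serum.

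Other provisions bear on the timing:

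- Appendix 1, Notes: "On treatment days, all assessments should be performed prior to dosing, unless otherwise specified".
- Section 4.5: "dosing will occur only if the clinical assessment and local laboratory test values are acceptable".
- Section 4.5.6.2 lists "Urine pregnancy test for women of childbearing potential" among the on-treatment local laboratory tests, without a date.
- Section 4.1.2.1, for entry: "Women of childbearing potential must have a negative serum pregnancy test result within 14 days prior to initiation of study treatment".
- Section 4.1.1.2: such women must be abstinent or "use a non-hormonal contraceptive method with a failure rate of" less than 1% per year.
- Section 5.4.3.1 instructs patients to report a pregnancy at once. Sections 4.6.1 and 5.4.3.1 require study drug to stop.
- Section 5.1.1.2.3 reports fetal toxicity and malformations with cobimetinib at exposures similar to those at 60 mg.

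**The concern.** The repeat test is the scheduled means of detecting an unrecognised pregnancy during treatment, and the rule to stop treatment works only once pregnancy is known. A window of ±2 weeks around the first day of a 28-day cycle is as wide as the cycle itself. A site can therefore dispense and start a cycle of a drug with a teratogenic signal without a current result and still comply with the protocol.

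The provisions that might prevent this do not. The rule on order before dosing governs the day on which the test is done; it does not require a test before the cycle's first dose. The dosing condition in Section 4.5 needs a result to judge, and neither it nor Section 4.5.6.2 says when the result must exist. The serum test protects only the start of treatment.

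The same ±2 weeks appears in footnotes k and o for LVEF and eye examinations, but those are at least three cycles apart (for LVEF, "on Day 1 of Cycles 5, 8, 11, 14, 17, and every 3 treatment cycles thereafter"). For the Cycle 2 examinations, both footnotes narrow the window to ±1 week.

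What is at stake is patient safety, through longer fetal exposure in a few patients. No efficacy analysis is affected.

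**Working it through.** **Inputs**

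- Cycle length 28 days; cobimetinib on Days 1 to 21, so 21 doses per cycle (Section 4.3.2.1; Appendix 1 footnote cc).
- Test window *w* = 14 days (footnote p); table default *w* = 3 days.
- Assumptions: cycles start on schedule, and a test on a dosing day comes before that day's dose.

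**Latest test in a cycle**

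Latest day = 1 + *w* = 1 + 14 = Day 15. Doses already taken, Days 1 to 14: 14 of 21, or 14/21 = 67%. If the test followed the Day 15 dose, the count would be 15.

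**Longest gap between consecutive tests**

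Gap = 28 + 2*w* = 28 + 14 + 14 = 56 days. This is a test on Day 15 of the preceding cycle, counted as one cycle's early test, followed by the next cycle's test on its own Day 15.

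**Scheduled cobimetinib doses within that gap**

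7 (Days 15 to 21) + 21 (the whole middle cycle) + 14 (Days 1 to 14) = 42.

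**Comparison of windows**

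| Window | Longest gap (days) | Doses between those tests | Doses of a cycle before its test |
|---|---|---|---|
| Exactly Day 1, before dosing | 28 | 21 | 0 |
| ±3 days | 28 + 3 + 3 = 34 | 21 + 3 = 24 | 3 |
| ±14 days (footnote p) | 56 | 42 | 14 |
| 3 days before to Day 1, before dosing | 28 + 3 = 31 | 21 | 0 |

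**Window as a share of the interval between assessments**

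- Pregnancy test: 28/28 = 100%.
- LVEF or eye examination every three cycles: 28/84 = 33%. For the later eye examinations, at four and six cycles, the share is smaller.

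**Expected number of pregnancies**

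The documents do not give the number of women of childbearing potential. Assume 5 to 25 of about 250 patients, one year each, at the 1% contraceptive-failure ceiling: 5 × 0.01 = 0.05 to 25 × 0.01 = 0.25.

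**The case against.** The text and arithmetic are not in dispute; the case against concerns how much they matter.

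**The 56 days is an isolated extreme.** It needs one test two weeks early and the next two weeks late. Two such gaps cannot be adjacent, consistently late testing still gives 28-day gaps, and the average stays at one test per cycle. The schedule also marks the test at the visit where cobimetinib is dispensed, so the extreme means not testing at two successive marked visits. This is right, and 56 days should be read only as a worst case. It does not touch the Day 15 point: a site that always tests late keeps 28-day gaps, but each cycle's test comes after 14 doses.

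**The expected number of pregnancies may be too high.** Base enrolment is 6 × 20 + 12 = 132, and one year per patient is probably long: the checkpoint-inhibitor studies in urothelial carcinoma cited in Section 1.1.2 report median PFS of 2.0 to 2.8 months. Sections 1.1.1 to 1.1.3 give median ages at diagnosis of 60 (head and neck) and 73 (urothelial) and male-to-female ratios of 2:1 to 3.5:1, which favour the low end. With the same 2% to 10% share, 132 patients and an assumed 3 months each, the result is 132 × 0.02 × 0.25 × 0.01 ≈ 0.007 to 132 × 0.10 × 0.25 × 0.01 ≈ 0.03. This stands as a plausible lower range and reinforces that few patients are affected.

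**Other flexibilities exist.** A note in Appendix 2 lets assessments move outside their window for holidays and unforeseen delays, and footnote aa allows ±7 days for study drug administration. If these apply here, the 31- and 34-day figures are not hard limits. But they only loosen the schedule further, and they do not supply the missing test before dosing.

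**It is a choice, not a breach.** Also fair: the protocol violates no standard that it states. The case for change rests on the seriousness of the possible harm and the small cost of preventing it.

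**Conclusion.** The concern holds. Footnote p overrides the ±3-day default, and no other provision requires a test before the first dose of Cycle 2 or any later cycle. A compliant test can follow 14 of the cycle's 21 doses, and the longest compliant gap is 56 days with 42 scheduled doses, twice the nominal figure in both respects. These figures assume cycles that start on time; a delayed cycle would lengthen the gap.

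This is a weakened backstop, not an absent one, because contraception, the screening serum test and self-report remain. The expected number of pregnancies is well below one under every assumption shown, but the possible harm to a fetus is serious and irreversible. The change should be made as an inexpensive safety improvement. It has no bearing on sample size or efficacy results.

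**What to change.** In footnote p, replace the ±2 weeks with a window that closes before dosing: test within 3 days before Day 1 dosing of each cycle, with a negative result required before cobimetinib is dispensed or dosed. Restoring ±3 days alone is not enough, because a Day 4 test after 3 doses would still comply. The footnote should also say how that day's atezolizumab infusion is handled while a positive urine result awaits serum confirmation.

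No test or visit is added. The test is already marked at the Day 1 visit where cobimetinib is dispensed, and footnote cc leaves room for an earlier test: "At least 7 days off cobimetinib are required prior to starting a new treatment cycle".

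The costs are less scheduling tolerance and a delay to that cycle's cobimetinib when a test is missed or a false-positive urine result is being confirmed. The edit is one footnote, but under Section 9.6 it needs ethics committee approval, and regulatory approval where locally required. It could be bundled with the next amendment.

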## Appendix 1 Schedule of Activities (cont.)

- 
- t Biopsy schedule for patients in Cohorts 1–6. Please see different biopsy schedule listed in the table for the biopsy cohort (Cohort 7). Fresh baseline tumor tissue collected during screening (or archival if fresh tumor biopsy cannot be performed); optional on-treatment biopsy at Cycle 1, Day 15 ( $\pm 5$  days); mandatory biopsy at progression if clinically feasible.
- u Mandatory pre-treatment biopsy
- v Biopsy Cohort 7, mandatory tumor biopsy done between Days 10 and 14 of Cycle 1.
- w Biopsy Cohort 7, second (mandatory) on-treatment biopsy will be done during Cycle 2, approximately 4–6 weeks after the first dose of atezolizumab.
- x Biopsy Cohort 7, optional post-treatment biopsy at the time of radiographic progression.
- y Biomarkers are collected until Cycle 3, Day 1 (including that visit) and then at treatment discontinuation.
- z Urine samples will be collected for urothelial carcinoma patients only: screening on Day 1 of Cycle 1; on Day 1 of Cycle 3; and at treatment discontinuation visit only.
- aa The initial dose of atezolizumab will be delivered over 60 ( $\pm 15$ ) minutes. If the first infusion is well tolerated, all subsequent infusions will be delivered over 30 ( $\pm 10$ ) minutes until loss of clinical benefit. Study drug administration may be  $\pm 7$  days.
- bb For patients in Cohorts 1–6 only.
- cc All patients will receive cobimetinib at a dose of 60 mg (three 20-mg tablets) orally once a day on Days 1–21 of each 28-day cycle. At least 7 days off cobimetinib are required prior to starting a new treatment cycle. Cobimetinib should be taken approximately the same time each day, and no later than 4 hours after the scheduled time.
-

## Appendix 2

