#### **4.3.2.2 Atezolizumab**

Atezolizumab will be given at a fixed dose of 840 mg by IV infusion on Days 1 and 15 of each 28-day cycle. A 28-day period is considered a treatment cycle.

Patients in the biopsy cohort, Cohort 7, will receive the first dose of atezolizumab of 840 mg by IV infusions on Day 15 of Cycle 1. Thereafter, they will receive atezolizumab 840 mg IV infusion Q2W on Days 1 and 15 of Cycle 2 and all subsequent cycles.

Administration of atezolizumab will be performed in a monitored setting where there is immediate access to trained personnel and adequate equipment and medicine to

manage potentially serious reactions. For anaphylaxis precautions, see [Appendix 7](#). Atezolizumab infusions will be administered per the instructions outlined in [Table 3](#).

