**Table 3 Administration of First and Subsequent Atezolizumab Infusions**

First Infusion	Subsequent Infusions
Premedication is not allowed.	If patient experienced IRR during any previous infusion, pre-medication with antihistamines, antipyretics, and/or analgesics may be administered for subsequent doses at the discretion of the treating physician.
Record vital signs (pulse rate, respiratory rate, blood pressure, and temperature) within 60 minutes before starting infusion.	Record patient's vital signs (pulse rate, respiratory rate, blood pressure, and temperature) within 60 minutes before starting infusion.
Infuse atezolizumab (one vial in 250 mL of NaCl) over 60 ( $\pm$ 15) minutes.	If the patient tolerated the first infusion well without infusion-associated adverse events, the second infusion may be delivered over 30 ( $\pm$ 10) minutes.
Record vital signs (pulse rate, respiratory rate, blood pressure, and temperature) during the infusion or after the infusion if clinically indicated.	If the patient had an IRR during the previous infusion, the subsequent infusion must be delivered over 60 ( $\pm$ 15) minutes.
Patients will be informed about the possibility of delayed post-infusion symptoms and instructed to contact their study physician if they develop such symptoms.	Record patient's vital signs (pulse rate, respiratory rate, blood pressure, and temperature) during the infusion or after the infusion if clinically indicated or if the patient experienced symptoms during the previous infusion.  If no reaction occurs, continue subsequent infusions over 30 ( $\pm$ 10) minutes using the same schedule for recording vital signs.

IRR=infusion-related reaction; NaCl=sodium chloride.

Dose modifications to atezolizumab are not permitted. Guidelines for treatment interruption of atezolizumab are provided in [Section 5.1.3.3](#), and the management of specific adverse events associated with cobimetinib and atezolizumab are provided in [Section 5.1.3.4](#). For information regarding management of atezolizumab-associated adverse events, refer to [Appendix 8](#).

For anaphylaxis precautions, see [Appendix 7](#).

See the pharmacy manual for detailed instructions on drug preparation, storage, and administration.

Any dose modification should be noted on the Study Drug Administration electronic Case Report Form (eCRF). Cases of accidental overdose or medication error, along with any associated adverse events, should be reported as described in [Section 5.4.4](#).

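### Appendix 1 footnote aa applies the 30-minute atezolizumab rate to every infusion after a tolerated first one, contradicting Table 3's 60-minute rule after an infusion-related reaction

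*Combined protocol and SAP*

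**What the plan says.** Section 4.3.2.2 sends the reader to Table 3: "Atezolizumab infusions will be administered per the instructions outlined in" that table. For subsequent infusions, Table 3 sets three rules on duration:

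- After a tolerated first infusion: "If the patient tolerated the first infusion well without infusion-associated adverse events, the second infusion may be delivered over 30" (±10) minutes.
- After a reaction: "If the patient had an IRR during the previous infusion, the subsequent infusion must be delivered over 60" (±15) minutes.
- Otherwise: "If no reaction occurs, continue subsequent infusions over 30" (±10) minutes.

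Table 3 also expects some patients to continue after a reaction: "If patient experienced IRR during any previous infusion, pre-medication with antihistamines, antipyretics, and/or analgesics may be administered for subsequent doses", at the treating physician's discretion.

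Appendix 1 footnote aa gives 60 (±15) minutes for the initial dose and then states: "If the first infusion is well tolerated, all subsequent infusions will be delivered over 30" (±10) minutes, for as long as clinical benefit lasts. It mentions neither reactions nor Table 3. The footnote mark is on the atezolizumab administration row and again on that row's Day 1 cell for Cycle 3 onward.

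Appendix 8 has its own IRR guidance. Its Table 4 acts by grade, but the text introducing it confines that guidance to Cycle 1 and leaves reactions in later cycles to institutional guidelines.

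**The concern.** Table 3 re-examines the rate at each infusion; the footnote settles it once, after the first. It also turns Table 3's permission (may) into a requirement (will). A site that works from the visit schedule could therefore give the infusion after a reaction at the faster rate, against a rule the protocol makes mandatory.

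No other text in the protocol backs that rule up. Appendix 8 Table 4 tells the site how to handle the infusion in progress and when to stop the drug, and for later infusions after a Grade 2 reaction it suggests premedication and close monitoring. It sets no duration for the next infusion. Among the texts available here, Table 3 is the only one that sets infusion time after an IRR, and the footnote leaves it out.

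**Working it through.** The plan states no figure on this point to reproduce. The check sets the two texts side by side and works out the windows.

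**Windows**

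- Footnote aa, every infusion after a tolerated first: 30 − 10 = 20 to 30 + 10 = 40 minutes.
- Table 3, the infusion after an IRR: 60 − 15 = 45 to 60 + 15 = 75 minutes.
- Overlap: the upper end of the first (40) is below the lower end of the second (45), so there is none. The nominal contrast is 30 against 60 minutes.

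**Where the texts agree and where they part**

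| Course of events | Footnote aa | Table 3 | Conflict |
|---|---|---|---|
| IRR at infusion 1, next is infusion 2 | condition not met, no rate given | 60 (±15) | no |
| No reaction at any infusion | 30 (±10) | 30 (±10) | no, apart from will/may at infusion 2 |
| Infusion 1 tolerated, IRR at infusion k ≥ 2, treatment continues, next is k + 1 | 30 (±10) | 60 (±15) | yes |

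**Earliest occurrence**

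With k = 2 the conflict first arises at infusion 3. Cohorts 1–6 are dosed on Days 1 and 15 from Cycle 1, so infusion 3 is Cycle 2 Day 1. A patient in Cohort 7 "will receive the first dose of atezolizumab of 840 mg by IV infusions on Day 15 of Cycle 1", so infusion 2 is Cycle 2 Day 1 and infusion 3 is Cycle 2 Day 15.

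**Who is affected**

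The triggering IRR is at infusion 2 or later. Infusion 2 falls in Cycle 1 (Day 15) only in Cohorts 1–6, so Appendix 8 Table 4, with its stop rule for Grade 3 or 4 reactions, governs only that one triggering infusion in those cohorts and none in Cohort 7. From Cycle 2 onward, institutional guidelines apply, and Table 5 in Section 5.1.3.4 requires all study treatment to stop after a severe hypersensitivity reaction. Patients who stop atezolizumab have no next infusion and drop out of the conflict. Everyone else with such a reaction is in it.

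**The case against.** The best defence is that the protocol already gives each text its role. Section 4.3.2.2 names Table 3 as the instruction on how to infuse, Section 4.5 uses Appendix 1 to say which activities are done and when, and Section 4.5.4 sends patients with an IRR at the previous infusion back to Section 4.3.2.2. On this reading the footnote abbreviates the no-reaction path, and Table 3's mandatory rule is the exception to it. Section 4.5 also requires a toxicity assessment before each dose. Finally, Table 3 is followed by "See the pharmacy manual for detailed instructions on drug preparation, storage, and administration", and that manual, which is not available here, may settle the matter.

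Most of this stands, and it is why the severity is low. It does not remove the inconsistency. The footnote says all and will, carries no pointer to Table 3, and sits on the row a site consults when giving the drug. Section 4.5 also makes Appendix 1 binding, and no general precedence clause is stated. The cross-reference in Section 4.5.4 appears under vital signs and not with the infusion schedule.

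Three stronger readings are tempting, and the documents do not support them:

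- That the protocol as a whole directs the faster rate after a reaction. It does not, because Section 4.3.2.2 names Table 3.
- That most infusions are exposed because the conflict can arise at any infusion from the third onward. That only counts positions in the schedule. Each case also needs an IRR at the infusion just before and continued treatment. The documents give no IRR incidence. The adverse event summary for the 150 patients in the Phase Ib combination study does not list IRR among events seen in at least 20% of patients, and it gives no rate below that threshold.
- That only Grade 1–2 reactions or approved re-challenges are affected. That would carry Appendix 8 Table 4 beyond Cycle 1, where its own introduction stops it.

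**Conclusion.** The inconsistency is real. Footnote aa, followed as written, cannot be reconciled with Table 3 for a patient who tolerates infusion 1, reacts at infusion 2 or later and continues atezolizumab: 20–40 minutes against 45–75, with no common value. The conclusion needs no assumption beyond the plain meaning of the two texts. No patient count or frequency is claimed.

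The consequence is confined to infusion safety and site compliance, and it arises only if a site relies on the footnote over Table 3. Response, survival, sample size and the planned analyses are untouched. Severity is low; the correction is worth making because it is simple and removes a route to breaching a mandatory safety instruction.

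**What to change.** Replace the rate rule in Appendix 1 footnote aa with: *Infuse per Table 3 (Section 4.3.2.2); if an IRR occurred at the previous infusion, deliver over 60 (±15) minutes.*

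This changes one footnote sentence. It adds no visit, procedure or patient, leaves the treatment intended by Table 3 as it is, and can be included in the next amendment. The pharmacy manual should be checked for the same shortened wording.
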